### 10.3. Statistical Analyses

#### 10.3.1. General Statistical Considerations

All data will be entered, verified, and archived by a contract research organization (CRO) external to Lilly and/or at Lilly. Data listings, summaries, and analyses will be performed by a CRO under the guidance and approval of statisticians at Lilly. Statistical analysis of this study will be the responsibility of Lilly.

Any change to the data-analysis methods described in the protocol will require an amendment ONLY if it changes a principal feature of the protocol. Any other change to the data analysis methods described in the protocol, and the justification for making the change, will be described in the statistical analysis plan and/or in the clinical study report. Additional exploratory analyses will be conducted as deemed appropriate.

Safety and efficacy analyses will be conducted on the full analysis set (FAS) or safety set. These sets include all data from all enrolled subjects who take at least 1 dose of study treatment.

All tests of treatment effects will be conducted at a 2-sided alpha level of 0.05, unless otherwise stated.

The planned statistical method for the primary analysis is the calculation of the estimate and the 95% confidence interval for the incidence of total (symptomatic or asymptomatic with FBG level  $\leq 54$  mg/dL [3.0 mmol/L]) hypoglycemic events at Week 24.

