#### 10.3.3. Efficacy Analyses

##### 10.3.3.1. Actual and Change from Baseline HbA1c

The actual and change in HbA1c level from baseline to Week 12 and Week 24 will be analyzed using descriptive statistics (mean, median, SD, SE, minimum, maximum, and number with missing values). For subjects requiring rescue medication (see Section 7.4), HbA1c values recorded after the first administration of rescue medication will not be considered for analysis, and these values will be considered as missing. In addition, for the actual value and change from baseline, a descriptive analysis using LOCF will be performed, using the baseline or 12-week value, if the 24-week value is missing or occurred after use of rescue medication.

Additionally, the change in HbA1c level from baseline to Week 24 will be analyzed using the general linear model for the FAS population. The general linear model will evaluate the change from baseline in HbA1c level as the dependent variable and the baseline value of HbA1c as covariate.

All the HbA1c analyses described will be repeated for the PPS population.

##### 10.3.3.2. Subjects Reaching HbA1c Targets ( $\leq 6.5\%$ or $< 7\%$ ) at Week 24

Subjects reaching HbA1c levels of  $\leq 6.5\%$  and  $< 7\%$  at Week 24 will be analyzed descriptively as binary variable, using number and percentage. The HbA1c values used to calculate this binary variable will be the LOCF value, that is, in case the Week 24 value is missing, the Week 12 value will be used. The denominator will be the total FAS population. Subject with missing HbA1c data at Week 12 and Week 24 will be considered as not having reached the target.

These analyses will be repeated for the PPS population.

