The above hypothesis will be tested based on α (alpha)=0.05, if the p-value \geq 0.05 then we will conclude that there is no statistically significant change in rates per 30 days and per subject year of total hypoglycaemic events. i.e. Ho is accepted. The sample SAS programme is as follows for negative binomial model:

proc genmod data=Dataset;

model Response Rate=Baseline_HbA1c / cl dist=NB link=log offset= offset variable;

estimate "Model with Mean baseline HbA1C for rate per 30 days and per year" int 1 Baseline HbA1c observed mean / exp;

ods output estimates=Output dataset;

run;

quit;

20.2.3 Incidence and rates per 30 days and per subject-year of nocturnal, severe, documented symptomatic and asymptomatic hypoglycemic events

Population: FAS and PPS

Stratification: Table: NA

Listing: NA

Statistics: By using the formula mentioned in section 20.1.2, we will get the Rates per 30 days and per subject year (365.25 days) between two time points (i.e. baseline to end of treatment/study) for each hypoglycaemic events category separately.

> The incidence and rates per 30 days and per subject-year for each below mentioned hypoglycemic events will be analysed similarly as mentioned in section 19.2.1 for incidence and section 20.2.2 for rates of hypoglycemic events.

- Nocturnal hypoglycemia
- Severe hypoglycemia
- Documented symptomatic hypoglycemia, and
- Asymptomatic hypoglycemia

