20.2.4 Change in HbA1c levels at Weeks 12 and 24 from baseline

| Population: | FAS and PPS |
|-----------------|-----------------|
| Stratification: | Table: By visit |

Listing: by subject

Statistics: The actual and change from baseline data of HbA1c levels will be summarised as (n, mean, standard deviation, standard error, median, minimum, maximum and number with missing values).

The change from baseline variable and the missing HbA1c results imputation i.e. LOCF will be done by using derivations mentioned in section 20.1.4 and the efficacy tables will be presented for with and without imputed values separately for each population set.

The change in HbA1c level from baseline to Week 12 and baseline to week 24 will be analysed using the general linear model.

The change from baseline in HbA1c level as dependent variable and the baseline value of HbA1c as covariate.

The estimate, 95% confidence interval and p-value will be summarised for efficacy table.

The regression line for the general linear model without categorical variable is as follows:

 $Y = \alpha + \beta (X)$

Where,

Y= The response change in HbA1c levels.

 $\alpha = Intercept$

 β =slope

X= Covariate i.e. Baseline HbA1c results

The hypothesis is as follows

H0: $\beta = 0$

i.e. There is no statistically significant change in HbA1c levels at week 12 and 24 from baseline depending on the baseline HbA1c.

V/s

H1: β ≠ 0

i.e. There is statistically significant change in HbA1c levels at week 12 and 24 from baseline depending on the baseline HbA1c.

The above hypothesis will be tested based on α (alpha)=0.05, if the p-value ≥ 0.05 then we will conclude that there is no statistically significant change in HbA1c levels at week 12 and 24 from baseline i.e. Ho is accepted.

The sample SAS programme is as follows:

proc mixed data=dataset;

model Y= X / s cl;

estimate "Model with Mean baseline HbA1C" int 1 HbA1c_baseline mean /CL;

ods output estimates=output dataset;

run; quit;

The listing of the HbA1c data will be provided containing the additional variable for identification of the HbA1C results measured after intake of rescue medication.

20.2.5 Percentage of subjects reaching HbA1c targets ≤6.5% and <7% at week 24

| Population: | FAS and PPS | |
|-----------------|--|--|
| Stratification: | Table: NA | |
| | Listing: NA | |
| Statistics: | Subjects reaching HbA1c levels of ≤6.5% and <7% at Week 24 will be identified as derivation mentioned in section 20.1.5. | |
| | | |

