20.2.6 Change in FBG levels at Weeks 4, 8, and 12 from baseline

Population: FAS and PPS

Stratification: Table: NA

Listing: By Subject

Statistics: The actual and change from baseline data of FBG levels will be summarised as (n, mean, standard deviation, standard error, median, minimum, maximum and number with missing values) and the listing will be presented.

The change from baseline of FBG level variable will be calculated by using formula mentioned in section 20.1.6.

The change from baseline variable and the missing FBG results imputation i.e. LOCF will be done by using derivations mentioned in section 20.1.6 and the efficacy tables will be presented for with and without imputed values separately for each population set.

The change in FBG level from baseline to Week 4,8 and 12 will be analysed using the general linear model.

The change from baseline in FBG level as dependent variable and the baseline value of FBG level as covariate.

The estimate, 95% confidence interval and p-value will be summarised for efficacy table.

The regression line for the general linear model without categorical variable is as follows:

 $Y = \alpha + \beta (X)$

Page 68 of 85

Where,

Y= The response change in FBG levels.

 $\alpha = Intercept$

```
\beta = slope
```

X= Covariate i.e. Baseline FBG results

The hypothesis is as follows

H0: $\beta = 0$

i.e. There is no statistically significant change in FBG levels at Week 4,8 and 12 from baseline depending on the baseline FBG level.

V/s

H1: β ≠ 0

i.e. There is statistically significant change in FBG levels at Week 4,8 and 12 from baseline depending on the baseline FBG level.

The above hypothesis will be tested based on α (alpha)=0.05, if the p-value \geq 0.05 then we will conclude that there is no statistically significant change in FBG levels at Week 4,8 and 12 from baseline i.e. Ho is accepted.

The sample SAS programme is as follows:

proc mixed data=dataset;

model Y= X / s cl;

estimate "Model with Mean baseline FBG" int 1 FBG baseline variable mean /CL;

ods output estimates=output dataset;

run;

quit;

Note: For the Change from FBG levels endpoint we are using the "7-point SMBG levels blood glucose parameter i.e. "Blood glucose concentration (mg/dL) upon awakening before breakfast (Fasting)" also, we have change form 7-point SMBG level endpoints (See section 20.2.8) i.e. we will get same results from both parameters.

20.2.7 Self-monitored 7-point SMBG levels at baseline, Weeks 4, 8, 12, and 24

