20.2.11 Change in weight and body mass index at Week 24 from baseline

| FAS and PPS |
|--|
| Table: By visit |
| Listing: By subject |
| The change in weight and body mass index at week 24 from |
| baseline will be summarised as (n, mean, standard deviation, |
| standard error, median, minimum, maximum) and the listing |
| will be presented. |
| |

The change from baseline of weight and body mass index variable will be calculated by using formula mentioned in section 20.1.11.

If the Week 24 result value for weight and body mass index is missing, then nearest previous visit value will be carried forward to week 24 results i.e. LOCF and Efficacy tables will be presented for with and without imputed values separately for each population set.

The change in weight and body mass index from baseline to Week 24 will be analysed using the general linear model.

The change from baseline in weight and body mass index as dependent variable and the baseline value of respective weight and body mass index as covariate.

The estimate, 95% confidence interval and p-value will be summarised for efficacy table.

The percentage change from baseline of weight in kg will also be summarised and efficacy table will be presented.

The regression line for the general linear model without categorical variable is as follows:

 $Y = \alpha + \beta (X)$

Where,

Y= The response change in weight and body mass index.

a =Intercept

 $\beta = slope$

X= Covariate i.e. Baseline weight and body mass index.

The hypothesis is as follows

H0: $\beta = 0$

i.e. There is no statistically significant change in weight and body mass index at Week 24 from baseline depending on the Baseline weight and body mass index.

V/s

H1: β ≠ 0

i.e. There is statistically significant change in weight and body mass index at Week 24 from baseline depending on the Baseline weight and body mass index.

The above hypothesis will be tested based on α (alpha)=0.05, if the p-value \geq 0.05 then we will conclude that there is no statistically significant change in weight and body mass index at Week 4,8,12 and 24 from baseline i.e. Ho is accepted. The sample SAS programme is as follows:

proc mixed data=dataset;

model Y= X / s cl;

estimate "Model with Mean baseline weight and body mass index " int 1 weight and BMI baseline variable mean /CL;

ods output estimates=output dataset; run; quit;

20.2.12 Change in Insulin Treatment Satisfaction Questionnaire (ITSQ) score at Week 24 from Week 4

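### The modelled 95% CIs for change from baseline hold only conditionally on the observed mean baseline; as intervals for the population mean change they are too narrow by a factor √(1−r²)

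*SAP*

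**What the plan says.** SAP 20.2.4 fits a straight line with one residual variance and no treatment factor: "The change from baseline in HbA1c level as dependent variable and the baseline value of HbA1c as covariate". The sample program is a PROC MIXED call with no RANDOM or REPEATED statement. An ESTIMATE statement then sets the covariate to its mean, "int 1 HbA1c_baseline mean /CL", and only the table of estimates is saved. For reporting, "The estimate, 95% confidence interval and p-value will be summarised for efficacy table".

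The same construction appears in 20.2.6 ("int 1 FBG baseline variable mean /CL") and 20.2.11 ("int 1 weight and BMI baseline variable mean /CL"). It is repeated in 17.2 (laboratory tests, on the Week -2 value), 18.2 (vital signs), 20.2.8 (7-point SMBG) and 20.2.12 (ITSQ, on the Week 4 value).

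Most of these sections also tabulate the unadjusted mean, SD and SE of change. None plans a confidence interval for the unadjusted mean. No section says that the model interval is conditional on the observed baselines; the nearest hint is the label on the ESTIMATE statement, which mentions the mean baseline.

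Protocol 10.3.3.1 names only the model and its covariate. It fixes neither the point of evaluation nor the standard error, so the issue arises in the SAP.

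**The concern.** In a two-arm trial, baseline adjustment removes variance from a contrast, and uncertainty about the mean baseline largely cancels between arms. Here there is one arm and no contrast. The line evaluated at the sample mean baseline is simply the raw mean change, but its model standard error leaves out the part of the variance that baseline explains. That part still contributes to the uncertainty, because another sample of patients would have a different mean baseline and therefore a different mean change.

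The objectives in SAP 2.2 concern a patient population, and readers will take a 95% CI for change in HbA1c as an interval for that population's mean change. Read that way, it overstates precision. On the same analysed subjects, the report would also show one point estimate with two different standard errors, descriptive and modelled, and no explanation of the difference.

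**Working it through.** **Inputs from the documents**
- Nominal level 95%; "All tests of treatment effects will be conducted at a 2-sided alpha level of 0.05, unless otherwise stated" (Protocol 10.3.1).
- Sample size: 200 completers and 20% drop-out (Protocol 10.1), so 200/0.80 = 250 enrolled, which reproduces the plan's figure.
- The plan gives no CI width or coverage for change from baseline beyond the nominal 95%, so there is no such figure to reproduce.

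**Assumed, because the documents are silent:** r = correlation of change with baseline, and an SD of change of 1.0 (used only to illustrate widths).

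**Derivation.** Let Y be change, X baseline and c the value entered in the ESTIMATE statement.
1. The estimate is α̂ + β̂c = Ȳ + β̂(c − X̄), with model variance s²_res·[1/n + (c − X̄)²/Sxx].
2. If c is the mean of the analysed subjects, c = X̄. The estimate is then Ȳ, with SE = s_res/√n on n − 2 df.
3. As an estimate of the population mean change, Var(Ȳ) = (σ²_res + β²σ²_X)/n = σ²_Y/n. The code omits β²σ²_X/n.
4. Since σ²_res = σ²_Y(1 − r²), SE(model)/SE(needed) = √(1 − r²).
5. Coverage of the population mean = 2·T(t₀.₉₇₅·√(1 − r²)) − 1, with T the t distribution function on n − 2 df.

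**Results at n = 200** (40,000 simulated trials per setting)

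| \|r\| | √(1−r²) | Coverage, formula | Coverage, simulated | Model CI width | One-sample t width |
|---|---|---|---|---|---|
| 0 | 1.000 | 95.0% | 94.9% | 0.278 | 0.278 |
| 0.3 | 0.954 | 93.9% | 94.0% | 0.266 | 0.279 |
| 0.5 | 0.866 | 91.1% | 90.9% | 0.241 | 0.279 |
| 0.7 | 0.714 | 83.9% | 83.9% | 0.199 | 0.279 |

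By formula, coverage at n = 250 agrees within 0.1 point. Truncating baseline to 7–11%, to mimic the HbA1c entry range, gives 94.0%, 91.0% and 84.1% for |r| = 0.3, 0.5 and 0.7. Across all settings the one-sample t interval covered the population mean 94.8–95.1% of the time. The SAP interval covered the mean conditional on the observed X̄ equally well, 94.8–95.1%.

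At |r| = 0.5 the two standard errors are 1/√200 = 0.071 (descriptive) and 0.866 × 0.071 = 0.061 (modelled).

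**Which r to expect.** If the baseline and Week 24 SDs are equal and ρ is the between-visit correlation, r = −√((1 − ρ)/2).
- ρ = 0.7, 0.5, 0.3: r = −0.39, −0.50, −0.59; coverage about 93%, 91%, 89%.
- ρ = 0.90, 0.95: r = −0.22, −0.16; coverage about 94.4%, 94.7%.
- |r| near 0.7 needs more than a moderate ρ. For example, a Week 24 SD of 0.8 times baseline with ρ = 0.3 gives r = −0.76/√1.16 = −0.71.

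**The case against.** The strongest reply is that regression inference is ordinarily conditional on the covariates, and that the SAP's label points to the expected change at the mean baseline. For that target the interval is sound, as the simulation confirms. This stands. What is missing is a statement that this is the target, when the objectives point to a population.

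A reader might also infer that the p-values are wrong. The documents do not support that as a general claim. The null hypothesis written in each section is β = 0, and the slope test does not involve the variance of the mean baseline. Only a p-value read from the ESTIMATE row, which tests whether the fitted change at the mean baseline is zero, would inherit the small standard error. The SAP saves the estimates table but states the slope hypothesis, so which p-value will be printed is unclear.

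The size rests on an r that the documents do not give, and one range cannot serve every endpoint. For reproducible measures such as weight and BMI the loss is well under one percentage point under the assumptions above. This also stands.

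The point estimate equals the descriptive mean only if the mean entered is that of the analysed subjects. The SAP does not say which mean is meant. If the FAS mean is entered while only observed values are modelled, the estimate shifts by β̂(c − X̄) and a small extra variance term appears. The variance is still residual only.

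Finally, the tabulated SD and SE of change already let a reader build the t interval for most endpoints. That softens the consequence but does not correct the printed interval.

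**Conclusion.** The point holds for the population mean change. In SAP 17.2, 18.2, 20.2.4, 20.2.6, 20.2.8, 20.2.11 and 20.2.12 the modelled CI is too narrow by √(1 − r²) whenever the slope on baseline is not zero. A nonzero slope is to be expected, because change contains minus the baseline value. With assumed equal SDs and between-visit correlations of 0.7 to 0.3, coverage is about 93% to 89%. The 84% figure belongs to the more extreme assumption |r| = 0.7.

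It would go too far to say that the intervals lack 95% coverage on any reading, or that every modelled change is materially affected. They are valid conditionally on the observed mean baseline, and for highly reproducible measures the loss is negligible.

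These are secondary and safety summaries with no decision rule attached to the CI. The primary analysis, a Clopper-Pearson interval for hypoglycaemia incidence (SAP 19.2.1), is untouched. The matter is worth correcting before the tables are produced, but it does not threaten the trial's main conclusion.

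**What to change.** In each of the seven sections, do one of the following:
- report the mean change with its one-sample t 95% CI, Ȳ ± t₀.₉₇₅,ₙ₋₁ × SD(change)/√n; or
- keep the model estimate and add β̂²·s²_X/n to its variance.

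Keep the regression to describe how change depends on baseline, and label any model interval that is retained as conditional on the observed mean baseline. State that the mean entered is that of the subjects in that analysis, and say whether the printed p-value is for the slope or for the ESTIMATE row.

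The cost is about one line of text and code per section, since mean, SD and n of change are already planned for most endpoints. For ITSQ, 20.2.12 lists descriptive statistics for the scores, so the SD of change must be added. Protocol 10.3.1 lets changes that leave the principal features intact be recorded in the SAP or study report, so a protocol amendment appears unnecessary. The downside is that the reported secondary intervals become somewhat wider.

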20.2.6 Change in FBG levels at Weeks 4, 8, and 12 from baseline

Population: FAS and PPS

Stratification: Table: NA

Listing: By Subject

Statistics: The actual and change from baseline data of FBG levels will be summarised as (n, mean, standard deviation, standard error, median, minimum, maximum and number with missing values) and the listing will be presented.

The change from baseline of FBG level variable will be calculated by using formula mentioned in section 20.1.6.

The change from baseline variable and the missing FBG results imputation i.e. LOCF will be done by using derivations mentioned in section 20.1.6 and the efficacy tables will be presented for with and without imputed values separately for each population set.

The change in FBG level from baseline to Week 4,8 and 12 will be analysed using the general linear model.

The change from baseline in FBG level as dependent variable and the baseline value of FBG level as covariate.

The estimate, 95% confidence interval and p-value will be summarised for efficacy table.

The regression line for the general linear model without categorical variable is as follows:

 $Y = \alpha + \beta (X)$

Page 68 of 85

Where,

Y= The response change in FBG levels.

 $\alpha = Intercept$

```
\beta = slope
```

X= Covariate i.e. Baseline FBG results

The hypothesis is as follows

H0: $\beta = 0$

i.e. There is no statistically significant change in FBG levels at Week 4,8 and 12 from baseline depending on the baseline FBG level.

V/s

H1: β ≠ 0

i.e. There is statistically significant change in FBG levels at Week 4,8 and 12 from baseline depending on the baseline FBG level.

The above hypothesis will be tested based on α (alpha)=0.05, if the p-value \geq 0.05 then we will conclude that there is no statistically significant change in FBG levels at Week 4,8 and 12 from baseline i.e. Ho is accepted.

The sample SAS programme is as follows:

proc mixed data=dataset;

model Y= X / s cl;

estimate "Model with Mean baseline FBG" int 1 FBG baseline variable mean /CL;

ods output estimates=output dataset;

run;

quit;

Note: For the Change from FBG levels endpoint we are using the "7-point SMBG levels blood glucose parameter i.e. "Blood glucose concentration (mg/dL) upon awakening before breakfast (Fasting)" also, we have change form 7-point SMBG level endpoints (See section 20.2.8) i.e. we will get same results from both parameters.

20.2.7 Self-monitored 7-point SMBG levels at baseline, Weeks 4, 8, 12, and 24

| Population: | FAS and PPS |
|-------------|-------------|
| | |

Stratification: Table: By visit

Listing: By subject

Statistics: Self-monitored 7-point SMBG levels at baseline, Weeks 4, 8, 12, and 24 will be summarised as (n, mean, standard deviation, standard error, median, minimum, maximum) for table and the listing will be presented.

20.2.8 Change in 7-point SMBG levels at Weeks 4, 8, 12, and 24 from baseline

| Population: | FAS and PPS |
|-----------------|-----------------|
| Stratification: | Table: By Visit |
| | Listing: NA |

Statistics: The change in 7-point SMBG levels at Weeks 4, 8, 12, and 24 from baseline will be summarised as (n, mean, standard deviation, standard error, median, minimum, maximum).

The change from baseline of 7-point SMBG levels variable will be calculated by using formula mentioned in section 20.1.8.

The change from baseline variable and the missing 7-point SMBG results imputation i.e. LOCF will be done by using derivations mentioned in section 20.1.8 and the efficacy tables will be presented for with and without imputed values separately for each population set.

The change in 7-point SMBG levels from baseline to Week 4,8 and 12 will be analysed using the general linear model.

The change from baseline in 7-point SMBG levels as dependent variable and the baseline value of 7-point SMBG levels as covariate.

The estimate, 95% confidence interval and p-value will be summarised for efficacy table.

The regression line for the general linear model without categorical variable is as follows:

 $Y = \alpha + \beta (X)$

Where,

Y= The response change in 7-point SMBG levels.

 $\alpha = Intercept$

 β =slope

X= Covariate i.e. Baseline 7-point SMBG levels.

The hypothesis is as follows

H0: $\beta = 0$

i.e. There is no statistically significant change in 7-point SMBG levels at Week 4,8,12 and 24 from baseline depending on the baseline 7-point SMBG level.

V/s

H1: β ≠ 0

i.e. There is statistically significant change in 7-point SMBG levels at Week 4,8,12 and 24 from baseline depending on the baseline 7-point SMBG level.

The above hypothesis will be tested based on α (alpha)=0.05, if the p-value \geq 0.05 then we will conclude that there is no statistically significant change in 7-point SMBG levels at Week 4,8,12 and 24 from baseline i.e. Ho is accepted.

The sample SAS programme is as follows:

proc mixed data=dataset;

model Y= X / s cl;

estimate "Model with Mean baseline 7-point SMBG levels " int 1 SMBG baseline variable mean /CL; ods output estimates=output dataset;

run;

Page 71 of 85

quit;

20.2.9 Intrasubject variability, as measured by the standard deviation (SD) of 7-point SMBG levels

| Population: | FAS and PPS |
|-----------------|---|
| Stratification: | Table: By visit |
| | Listing: NA |
| Statistics: | Intrasubject variability will be calculated by using formula mentioned in section 20.1.9 and this intrasubject variability will be presented for table. |

